2.1. Summary of the Proposed Study

This protocol is for a randomized, double-blind, active placebo controlled study of the safety and efficacy of 3,4-methylenedioxymethamphetamine MDMA-assisted psychotherapy in patients with treatment-resistant posttraumatic stress disorder (PTSD). In this study, 12 patients will receive either an active placebo dose or a fully active dose of MDMA during three experimental psychotherapy sessions, each six to eight hours long, scheduled three to five weeks apart. Participants assigned to receive the active placebo and participants assigned to receive the fully active dose will receive the same course of psychotherapy, which consists of two introductory sessions prior to the first experimental (active placebo or fully active dose MDMA) session, follow-up psychotherapy sessions occurring a day after each experimental session, and two to four integrative psychotherapy sessions conducted on a weekly basis after each experimental session, with the first of these sessions scheduled a week after each experimental session. Active placebo will be 25 mg MDMA followed two and a half hours later by 12.5 mg, and the fully active dose will be 125 mg followed two and a half hours later by 62.5 mg. Extent of PTSD symptoms will be assessed by an independent rater at baseline, 3 weeks after the second and third experimental session and two, six and 12 months after the third MDMA-assisted session. The Clinician Administered PTSD Scale (CAPS) will serve as the primary outcome measure. We hypothesize that PTSD symptoms will be reduced in participants receiving the fully active dose of MDMA, that MDMA-assisted psychotherapy will be well-tolerated and will not produce serious adverse effects in this population, that three experimental sessions will lead to better results than two sessions, and that results are stable at the follow up assessments at 2, 6 and 12 months after the last experimental session.

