With participants carefully monitored for any indicators of adverse events, the initial doses of either 125 mg or 150 mg, and the cumulative dose of 187.5 mg or 225 mg respectively will prove to be tolerable and pose no more than minimal risk. The side effect profile is expected to increase with the higher dose but it is considered unlikely that there will be any Serious Adverse Events (SAEs) or any persisting side effects.

Table 1. Dose Regimen

	Initial Dose	Supplemental Dose	Cumulative Dose
Low Dose	25 mg	12.5 mg	37.5 mg
Fully Active Dose	125 mg	62.5 mg	187.5 mg
20% Larger Active Dose	150 mg	75 mg	225 mg

Supplemental doses for both the Low and the Fully Active dose conditions were chosen to be half the size of initial doses, and the dosage and schedule of dosing was chosen on the basis of case reports describing the use of MDMA in psychotherapy (Greer and Tolbert 1998; Stolaroff 2004, Styk 2007). Supplemental dosing performed 2.5 hours after the initial dose is expected to extend the course of drug effects without increasing their intensity. Both the Low and Fully Active dose conditions use supplemental doses that are half of the initial dose, to make dosing schedule equivalent across the conditions.

Participants will receive an initial dose of MDMA approximately 1 to 1.5 hours after they arrive at [name] office for each experimental session. If the investigators believe the participant is able to tolerate a supplemental dose and the participant agrees to take it, then a supplemental dose will be offered 2.5 hours later. The investigators will not administer the supplemental dose if the participant is exhibiting signs or symptoms that would place him or her at greater risk of experiencing a serious adverse event.

Each dose will consist of the specified amount of racemic MDMA mixed with an inactive substance, such as lactose, to prevent the investigators from distinguishing doses through weight or appearance of the capsules. Initial doses will be distinguished from supplemental doses through labeling them "Dose 1" and "Dose 2" or "first" and "second" dose to ensure that the correct dose is administered at the scheduled time. Each dose of MDMA will be administered along with 250 to 300 mL electrolyte-containing fluid. MDMA will be administered during each of the three experimental sessions, with the second and third session scheduled to fall two to four weeks after the previous experimental session.

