2.8.2. Assessments and Measures

Psychiatric diagnoses will be made through the Structured Clinical Interview for Diagnoses (SCID), and PTSD symptoms will be measured by the Clinician Administered PTSD Scale (CAPS) during screening to determine whether an individual may participate in the study.

PTSD symptoms will be assessed six times in this study:

- T0: *Baseline assessment*
- T1: *Post MDMA 2 assessment*: 3 weeks after the second experimental session (MDMA 2)
- T2: *End of treatment assessment*: 3 weeks after the third experimental session (MDMA 3)
- T3: *1st follow-up assessment*: 2 months after the third experimental session (MDMA 3)

T4: *2nd follow-up assessment*: 6 months after the third experimental session (MDMA 3) for all participants assigned to the Fully Active Dose condition, and all participants assigned to the Low Dose condition who choose not to take part in the open-label study continuation.

T5: *3rd follow-up assessment*: 12 months after the third experimental session (MDMA 3) for all participants assigned to the Fully Active Dose condition, and all participants assigned to the Low Dose condition who choose not to take part in the open-label study continuation.

Participants who choose to take part in the open label study continuation “Stage 2” will be assessed identically to stage 1 three weeks after the second and third (end of treatment) experimental sessions and two, six and twelve months after the third experimental session in Stage 2. The T2 assessment will serve as baseline for stage 2.

Participants who choose to take part in the open label study continuation “Stage 3” will be assessed identically to stage 1 three weeks after the second (end of treatment) experimental session and two, six and twelve months after the experimental session in Stage 2. The T3 assessment will serve as baseline for stage 3.

All outcome measures will be administered by an independent assessor. The independent assessor will remain blind to subject condition and will not be present during psychotherapy sessions. The CAPS will serve as the primary outcome measure, and the PDS will serve as additional measure of PTSD symptoms. The CAPS and the PDS are specifically designed to assess PTSD. German versions of all measures will be used in this study.

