2.8.6. Open Label Continuation for Active Placebo Patients ("Stage 2")

After each participant completes all outcome measures on the session scheduled 3 weeks after the third experimental session (T2), the participant will have a 30-minute meeting with the principal investigator. During this meeting, the blind will be broken for the individual participant while retaining the blind for the independent assessor. If a participant had received the Low (25 mg followed 2.5 hours later by 12.5 mg) dose of MDMA during the course of the study, she or he would be offered an opportunity to enroll in the open label continuation of the study, referred to as Stage 2. He or she would give written informed consent to take part in this second stage of the study, with consent given separately from the initial consent. If the participant consents to take part in Stage 2 of the study, he or she would receive the Fully Active dose of MDMA (125 mg followed 2.5 hours later by 62.5 mg) during three experimental sessions scheduled two to four weeks apart. Outcome measures administered three weeks after the third experimental session will serve as baseline measures for Stage 2. The participant would undergo one preparatory non-drug psychotherapy session 1 to 2 weeks prior to the first experimental session, and he or she would receive non-drug psychotherapy follow-up sessions according to the same schedule described for the active placebo controlled study. Procedures for non-drug psychotherapy sessions, experimental sessions, weekly telephone contact and outcome measure administration will be the same as those employed in the first stage of the study.

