The subject will be required to give written informed consent to take part in Stage 3 of the study, with consent given separately from the initial consent. If the participant consents to take part in Stage 3 of the study, he or she would receive an initial dose of MDMA that will either be identical to that used in Stage 1 and 2 or that of 150 mg, followed by a supplemental dose of up to 75 mg 2.5 hours later, during two experimental sessions scheduled two to four weeks apart. The investigators will use clinical judgment as the basis for determining initial and supplemental dose for each of the two Stage 3 sessions, and they may use their judgment to employ a different dose during the second session on the basis of their experience during the first Stage 3 session. Outcome measures administered 2 months (T3) after the third experimental session will serve as baseline measures for Stage 3. The participant would undergo one preparatory non-drug psychotherapy session 1 to 2 weeks prior to the first experimental session, and he or she would receive non-drug psychotherapy follow-up sessions according to the same schedule described for stage 1 of the controlled study. Procedures for non-drug psychotherapy sessions, experimental sessions, weekly telephone contact and outcome measure administration will be the same as those employed in the first stage of the study.

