In order to avoid dehydration, participants will be encouraged to drink 750 - 1500 ml. of Gatorade or a similar electrolyte-containing fluid during the session depending on their size, level of activity and body temperature.

Hyponatremia:

Participants will be given electrolyte solutions such as Gatorade instead of water in order to decrease the likelihood of dilutional hyponatremia. They will not be allowed to drink more than 3 L. of fluids over the course of the experimental session, and fluid intake will be spread out appropriately during the session. If there are any signs or symptoms of hyponatremia such as confusion, vomiting, myoclonus or ataxia, a stat serum sodium will be drawn and fluids will be withheld until the results are obtained. If the serum sodium is less than 125mEq/L, serum and urine osmolality and sodium will be measured, If serum sodium is less than 125mEq/L, serum and urine osmolality and sodium will be measured, and the subject will be transported to the ICU.

If a participant had low serum sodium during the experimental session and exhibited signs of clinically significant hyponatremia, then the principal investigator will not enroll the participant in any subsequent experimental sessions unless, in the clinical judgment of the investigators, further fluid restriction during the second experimental session would be a sufficient means of preventing hyponatremia.

Liver toxicity:

Liver enzymes will be measured as part of the initial screening visit. Volunteers with pre-existing abnormalities will be excluded from the study. If a participant exhibits signs of liver toxicity after an experimental session, then he or she will not receive a subsequent experimental session.

Neuropsychological toxicity:

Psychological and neurological status will be clinically monitored by the therapists during MDMA sessions and during therapy sessions at frequent intervals thereafter. If, on clinical examination after each experimental session, a participant is found to have cognitive deficits that persist for more than two weeks, this participant will not be given a subsequent experimental session.

Abuse and dependence:

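### At the two-week minimum gap allowed in Stage 3, the cognitive-deficit stop rule cannot act before the second dose, and no other mandatory rule holds that dose

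*Protocol*

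**What the plan says.** The neuropsychological paragraph of Protocol 2.8.8 has the therapists monitor psychological and neurological status during and after sessions. It then sets one mandatory stop: if a participant is "found to have cognitive deficits that persist for more than two weeks, this participant will not be given a subsequent experimental session".

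The session interval is stated in several places:

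- **Stage 3 (2.8.7):** MDMA is given "during two experimental sessions scheduled two to four weeks apart". This is the only interval stated for Stage 3. The dose may reach 150 mg plus 75 mg, and 2.8.7 says of the investigators that "they may use their judgment to employ a different dose during the second session".
- **Stage 2 (2.8.6):** "during three experimental sessions scheduled two to four weeks apart". Section 2.1, however, says that Stage 2 has the same structure as Stage 1.
- **Stage 1:** 2.8.1 has three sessions, "with the second and third session scheduled to fall two to four weeks after the previous experimental session". Sections 2.1, 2.5 and 2.8.4 give three to five weeks, and SAP 4.0 describes Stage 1 that way.

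Stage 3 participants also receive "non-drug psychotherapy follow-up sessions according to the same schedule described for stage 1 of the controlled study". For Stage 1, section 2.1 describes that schedule as "two to four integrative psychotherapy sessions conducted on a weekly basis after each experimental session", with the first visit one week after dosing.

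**The concern.** The threshold of the stop rule, two weeks, equals the shortest gap that 2.8.7 allows between doses. The rule asks for a duration strictly longer than that, so at the shortest gap a deficit caused by one session cannot have lasted long enough to block the next.

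Stage 3 has only two sessions. At a 14-day gap the rule therefore cannot act at all on a deficit that arises in that stage, and the second dose may be higher than the first. In Stages 1 and 2, if the two-week text is followed, the rule acts one dose late: it can first bar session 3, not session 2.

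**Working it through.** The plan gives no figure of its own on this point, so the check is day-and-hour arithmetic followed by a search for another rule that would hold the dose.

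**1. Inputs.** The threshold is more than two weeks (2.8.8). The minimum gap is two weeks (2.8.7; also 2.8.6 and 2.8.1). Sessions start at 10:00 after a 9:00 arrival and last six to eight hours (2.8.5.1).

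**2. Longest possible deficit at the next dose, 14-day gap.**
- Threshold: 14 × 24 = 336 h, to be exceeded.
- Counted from the previous 10:00 dose: 14 × 24 = 336 h. Not exceeded.
- Counted from the end of a six-hour session (16:00): 336 − 6 = 330 h. Not exceeded.
- At the 9:00 check-in on the dosing day: 336 − 1 = 335 h, or 13.96 days. Not exceeded.

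**3. Sensitivity to clock time.** Section 2.8.1 puts the dose 1 to 1.5 h after arrival. A 10:00 dose followed by a 10:30 dose gives 336.5 h between doses. Section 2.8.5 puts drug onset at 30 minutes at the earliest, so an effect of the first dose can have lasted 336.5 − 0.5 = 336 h. The result then depends on counting from onset.

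**4. The same calculation at three weeks.** From dose: 21 × 24 = 504 h, past the threshold by 504 − 336 = 168 h. From session end: 504 − 6 = 498 h, past it by 498 − 336 = 162 h. The rule can be met, but only for early onset. At the 9:00 check-in on day 21, 20.96 days have passed, so the deficit must have begun before day 20.96 − 14 = 6.96. A deficit starting on day 8 has lasted 21 − 8 = 13 days and does not trigger the rule.

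**5. Other rules that might hold the dose.** The other bars in 2.8.8 cover sustained blood pressure or heart rate, mania or psychosis, temperature, hyponatremia (with an exception by judgment) and liver toxicity. Suspension until recovery applies only to hospitalization after severe panic. The stroke paragraph requires hospital transfer for neurological deficits and is silent on the next session. The stated pre-dose condition in 2.8.5.1 is negative urine tests. None of these covers a cognitive deficit that is still present but has lasted two weeks or less. Section 2.7 lets the investigators withdraw anyone for any reason, which is permission and not a requirement.

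**6. Intervals at which a two-week gap could occur.** In Stages 1 and 2 the T1 assessment falls 21 days after session 2, so a two-week gap before session 3 would put T1 after that session. Only the gap between sessions 1 and 2 is exposed. Stage 3 has no assessment between its two sessions.
- Stage 3: (2 − 1) × 3 participants (SAP 4.0) = 3.
- Stage 2, if 2.8.6 is followed: 1 × up to 4 low-dose participants = up to 4.
- Stage 1, if 2.8.1 is followed: 1 × 12 = up to 12.
- Maximum 3 + 4 + 12 = 19, of which 16 depend on how the interval conflict is resolved.

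**The case against.** The best case against this is that it holds at one point of the window only. From day 15 the rule can be met, and the margin at day 14 comes down to half an hour in a plan written in weeks. That is correct, and the point is limited accordingly.

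A literal 14-day gap also sits badly with the therapy schedule. At least two weekly integrative visits follow each dose, at about days 7 and 14. Section 2.8.5 says goals for the following MDMA session are reconsidered in them, so they are meant to come first. The second visit would compete with the dosing morning. This makes a 14-day gap unlikely, but no text bars it, and two weeks is the protocol's own lower bound.

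There is also room for judgment. Therapists meet the participant before dosing, inclusion item 13 in 2.7.1 provides for delayed sessions, and SAP 4.0 makes Stage 3 dosing subject to safety parameters that it does not define. These allow a dose to be held; none requires it for a cognitive deficit.

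A reader might go further and infer that the stop rule is inert throughout the trial, or that participants were re-dosed with unresolved deficits. The documents support neither. The rule works from day 15 and at every three-to-five-week interval, for deficits that begin early enough. Actual gaps are not reported. No rate of cognitive deficits lasting two weeks is given, and 2.2.2 considers lasting deficits unlikely. Nor is 19 a count of exposed participants; it is a ceiling on intervals.

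**Conclusion.** The point holds in a narrow form. At the two-week lower bound in 2.8.7, the 2.8.8 rule cannot stop the second Stage 3 dose for a deficit caused by the first, and no other mandatory rule does so. The conclusion assumes that two weeks means 14 days and that a deficit is counted from drug onset or later.

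The unconditional size is three Stage 3 intervals of unreported length, in a stage later cancelled under Amendment 5. Up to 16 further intervals count only if 2.8.1 and 2.8.6 prevail over 2.1, 2.5 and 2.8.4. No expected number of affected participants can be given. The correction is still worth making: the protocol chose a mandatory rule for this risk, and the repair is cheap.

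**What to change.** **Main change.** Add to 2.8.8: *No experimental session will be given while any cognitive deficit noted since the previous session is unresolved; a therapist will check and record this before dosing.* This works at any interval and leaves the existing two-week bar in place. Changing the threshold to two weeks or more would not do, because at a 14-day gap it is still unmet at the 9:00 check-in (13.96 days).

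**Second change.** Replace two to four weeks with three to five weeks in 2.8.1, 2.8.6 and 2.8.7. For Stages 1 and 2 this removes the conflict; for Stage 3 it extends the Stage 1 interval. Alone it is only partial, since a deficit starting after about day 7 would still not trigger the rule by day 21.

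**Cost.** The first change needs a brief recorded check at a meeting that already takes place, and a postponed session where a deficit is unresolved. The second delays treatment by at most 21 − 14 = 7 days, once per participant in each stage. Where 2.7.1 item 6 requires abstinence until T3, time off psychotropic medication grows by the same amount. Table 2 already plots the Stage 1 sessions three weeks apart, at weeks 3, 6 and 9.

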4.1. Primary Pharmacodynamics

MDMA interacts with plasma monoamine transporters and storage vesicles to increase extracellular levels of 5-HT, dopamine, and norepinephrine (Cozzi et al. 1999; Fitzgerald and Reid 1990; Gudelsky and Nash 1996; Hiramatsu and Cho 1990; Kankaanpaa et al. 1998; Nash and Brodkin 1991; Rudnick and Wall 1992; Schuldiner et al. 1993). Direct MDMA stimulation of postsynaptic 5-HT_{2A} receptors and α-2 adrenoceptors also contributes to MDMA's effects. For example, dopamine release is also indirectly increased by MDMA stimulation of 5-HT_{2A} receptors on GABAergic striatonigral neurons (Gudelsky and Nash 1996; Koch and Galloway 1997; Palfreyman et al. 1993; Schmidt et al. 1992; Yamamoto et al. 1995).

Although the specific mechanisms of MDMA's therapeutic effects are not fully understood, several observations and hypotheses can be made. Increased extracellular levels of dopamine and norepinephrine are known to be important to the reinforcing effects of psychostimulants (Ritz and Kuhar 1993; Rothman et al. 2001; Wise and Bozarth 1985). These neurotransmitters likely play a

similar role with MDMA, producing feelings of excitement, euphoria, and well-being. When the D₂ receptor antagonist haloperidol was combined with MDMA, human volunteers reported less positive mood and greater anxiety (Liechti and Vollenweider 2000a), findings in keeping with these hypotheses. Central dopamine and norepinephrine are also thought to regulate readiness for action and arousal, with dopamine possibly mediating behavioral readiness, and locus coeruleus norepinephrine mediating conscious registration of external stimuli (Clark et al. 1987; Robbins and Everitt 2000). Increasing these neurotransmitters may therefore place the individual in a state of alertness that is ideal for recalling or even re-experiencing state-dependent memories of stressful events. This potentially aversive state may be modified by MDMA effects on both the serotonergic system and postsynaptic α-2 adrenoceptors.

MDMA effects on the serotonergic system are likely important for its therapeutic effects. MDMA induces 5-HT release and is a mild 5-HT_{2A} agonist. Serotonergic dysfunction is associated with anxiety, aggression, and depression. Increasing 5-HT release is thought to have opposite effects. For example, stimulation of 5-HT_{1A} and 5-HT_{1B} receptors decreases anxiety and aggression in rodent behavioral studies (Brunner and Hen 1997; Graeff et al. 1996) and likely contributes to reduced defensiveness and increased self-confidence reported after MDMA. 5-HT_{1A} receptors in the hippocampus have also been specifically hypothesized to enable disengaging from previously learned associations if they lead to adverse outcomes (Guimaraes et al. 1993). MDMA also has moderate 5-HT_{2A} activity (Nash et al. 1994), which leads to modest alterations in perception of meaning (Liechti et al. 2000b), possibly facilitating new ways of thinking. Case reports suggest increasing extracellular 5-HT levels may facilitate recovery of remote memories (Robertson 1997), a phenomenon that has been reported by psychotherapists administering MDMA to patients (Downing 1986). Studies in humans suggest that serotonergic activity plays an important role in generating the subjective effects of MDMA, since co-administration of a serotonin uptake inhibitor reduces most subjective effects (Liechti et al. 2000a; Tancer and Johanson 2004). Thus, MDMA effects on the serotonergic system may decrease anxiety and aggression and create a state of mind that is conducive to psychotherapy.

Direct MDMA stimulation of postsynaptic α-2 adrenoceptors may modify this state by altering the balance of α-1 and α-2 stimulation, allowing the individual to remain emotionally calm despite noradrenergic activation. MDMA is an α-2 agonist (Lavelle et al. 1999). Like other α-2 agonists, such as guanfacine and clonidine (Franowicz 1998), MDMA produces feelings of calmness and relaxation (Cami et al. 2000). Open label trials suggest that clonidine may be helpful for treating symptoms of PTSD (Harmon and Riggs 1996; Kinzie and Leung 1989), indicating that α-adrenergic action may possess anxiolytic effects in humans.

